### **5.7.2. Immunogenicity (Antibodies to Bermekimab)**

Blood samples will be collected to examine the formation of antibodies to bermekimab at the specified visits as shown in the schedule of activities in the protocol. Samples will also be collected at the final visit from participants who terminate study participation early.

Immunogenicity analyses will be based on the Immunogenicity Analysis Set (Section 4). No imputation for missing concentration data will be performed.

The antibodies to bermekimab status (positive, negative) and titers will be summarized by treatment group for participants who receive at least one dose of bermekimab and have appropriate samples for detection of antibodies to bermekimab. The maximum titers of antibodies to bermekimab will be provided for participants who are positive for antibodies to bermekimab.

A listing of participants who are positive for antibodies to bermekimab will be provided. This listing will provide information regarding dose administered, bermekimab concentration, and antibody status for all visits.

In addition, to explore the relationship between antibodies to bermekimab status and serum bermekimab concentrations, and safety, the following analysis may be performed as appropriate:

- Summary of injection-site reactions by antibody to bermekimab status
- Summary of serum bermekimab concentrations by antibody to bermekimab status
- Plots of median (IQ) serum bermekimab concentrations over time by antibody to bermekimab status

### **5.8. Interim Analyses**

An internal independent interim analysis committee (IAC) will be established to review the interim data to formulate recommended decisions and/or actions in accordance with the objectives of the interim analyses. The IAC will consist of at least a clinician and a statistician (neither of whom are involved in study conduct), one of whom will chair the committee, and other members as required.

The IAC will review the unblinded efficacy data and provide recommendations about the next step of enrollment of Part 2 portion of this study based upon the results of the first (when approximately 50% of the Part 1 participants reach Week 16) and/or second (when 100% of the Part 1 participants reach Week 16) interim efficacy analyses. Both interim analyses will be performed to determine

whether the efficacy of bermekimab, as measured by the proportion of participants achieving HiSCR50 response at Week 16, is sufficient to open the enrollment of the Part 2 portion of the study. Other selected supportive efficacy endpoints could also be reviewed. Additionally, as part of both IAs, serum bermekimab concentration data available at the time of both database release will be used for PK concentration analyses and population PK analysis to support IAC data review and to inform dose regimens for Phase 2b portion of the study.

Based on the results from the first IA, consideration of termination of the study may be warranted if either the efficacy is sufficiently low based on the prespecified criteria or the efficacy is considered to be insufficient to outweigh specific safety findings observed in study participants.

Furthermore, if the study is not terminated after the 1st IA, a database lock based on all available data when 100% of participants completed Week 16 from Part a portion of the study will be planned to support the end of phase 2 meeting. The unblinded results will be limited to specific sponsor personnel not involved in the study conduct. Interim analysis results will not be disseminated to investigators or individuals associated with the conduct of the study.

Following the first IA, the study was terminated due to futility.

### **5.9. Data Monitoring Committee (DMC)**

An external iDMC whose members are not directly involved in the conduct of 77474462HDS2001 Phase 2a/2b study, will review unblinded safety data to ensure the safety of the participants enrolled in this study. The iDMC will convene for a prespecified look at safety after at least 12 participants have received 4 weekly doses. The committee will also meet regularly to review unblinded safety data. After the review, the DMC will make recommendations to the sponsor regarding the conduct of the study. The DMC will consist of at least one clinical physician and one statistician, not involved in the conduct of the study. DMC responsibilities, authorities, and procedures will be documented in the DMC charter.

## 6. SUPPORTING DOCUMENTATION

### 6.1. Appendix 1 List of Abbreviations

ADA	anti-drug antibody
AE	adverse event
ALT/SGPT	alanine aminotransferase
AST/SGOT	aspartate aminotransferase
ATC	anatomic and therapeutic class
BMI	body mass index
BSA	body surface area
CI	confidence interval
CRF	case report form
CSR	Clinical Study Report
CTCAE	Common Terminology Criteria for Adverse Events
CV	coefficient of variation
DMC	Data Monitoring Committee
DPS	Data Presentation Specifications
eCRF	electronic case report form
FAS	full analysis set
FDA	Food and Drug Administration
IQ	interquartile
IWRS	interactive web response system
LLOQ	lower limit of quantification
MedDRA	Medical Dictionary for Regulatory Activities
MMRM	Mixed-Effect Model Repeated Measure
NAb	neutralizing antibodies
PD	pharmacodynamic(s)
PI	principal investigator
PK	pharmacokinetic(s)
SAE	serious adverse event
SAP	Statistical Analysis Plan
SD	standard deviation
TEAE	treatment-emergent adverse event
US NCI	United States National Cancer Institute
WHO	World Health Organization

**6.2. Appendix 2 Changes to Protocol-Planned Analyses**

The IA futility criterion was met and the decision was made to terminate the study. The SAP has reduced efficacy, safety and PK analyses.

### 6.3. Appendix 3 Demographics and Baseline Characteristics

The number of participants in each analysis set will be summarized and listed by intervention group, combined active intervention group, and overall. In addition, the distribution of participants by region, country, and site ID will be presented unless otherwise noted.

Table 7 presents a list of the demographic variables that will be summarized by intervention group, combined active intervention group, and overall for the FAS analysis set.

**Table 7: Demographic Variables**

Continuous Variables:	Summary Type
Age (years)	Descriptive statistics (N, mean, standard deviation [SD], median and range [minimum and maximum], and IQ range).
Weight (kg)	
Height (cm)	
Body Mass Index (BMI) (kg/m  )	
Body Surface Area (BSA) (m  )	
Categorical Variables	Frequency distribution with the number and percentage of participants in each category.
Age (<40 years, 40-64 years, and ≥65 years)	
Sex (male, female)	
Weight (<95 kg, ≥95 kg)	
Race (American Indian or Alaska Native, Asian, Black or African American, Native Hawaiian or other Pacific Islander, White, Multiple)	
Ethnicity (Hispanic or Latino, not Hispanic or Latino)	
BMI ([normal <25 kg/m  , overweight 25-<30 kg/m  , obese ≥30 kg/m  ])	

aIf multiple race categories are indicated, the Race is recorded as 'Multiple'

Baseline disease characteristics (e.g., duration of HS disease, baseline Hurley stage status, baseline AN count, inflammatory nodule count, abscess count, and draining fistula, baseline IHS4, baseline HASI, HS-IGA, and PRO related measurements) will be summarized by treatment group. In addition, summaries of participants' medical history and current diagnoses, alcohol intake, and smoking status will be provided by treatment group and the distribution of participants by Hurley stage status (II, and III) will also be provided.

#### **6.4. Appendix 4 Protocol Deviations**

In general, the following list of major protocol deviations may have the potential to impact participants' rights, safety or well-being, or the integrity and/or result of the clinical study. Participants with major protocol deviations will be identified prior to database lock and the participants with major protocol deviations will be summarized by category through Week 16 and through the end of study.

- Developed withdrawal criteria but not withdrawn
- Entered but did not satisfy criteria
- Received a disallowed concomitant treatment
- Received wrong treatment or incorrect dose
- Other

A listing of participants with major protocol deviations and a listing of patients who missed scheduled study agent administration will also be provided by randomized treatment group. In addition, analyses of COVID-19 related protocol deviations will be provided.

## 6.5. Appendix 5 Prior and Concomitant Medications

Prior medications are defined as any therapy used before the day of first dose (partial or complete) of study intervention. Prior HS treatment received (including prior HS related surgery) will be summarized by randomized treatment group for the FAS.

Concomitant medications will be coded using the World Health Organization Drug Dictionary (WHO-DD). Concomitant medications are defined as any therapy used on or after the same day as the first dose of study intervention, including those that started before and continue on after the first dose of study intervention.

Summaries of concomitant medications will be presented by anatomic and therapeutic class (ATC) term, and intervention group. The proportion of participants who receive each concomitant medication will be summarized as well as the proportion of participants who receive at least 1 concomitant medication.

In addition, a list of participants who received a protocol-prohibited medication or therapy meeting the definition of ICE 2 will be provided.

**6.6. Appendix 7 Intervention Compliance**

Study agent compliance will be summarized descriptively through Week 31 for the FAS. Compliance to randomized intervention versus actual intervention will be presented in a summary table. Number of the participants receiving each scheduled treatment will be summarized.

## **6.7. Appendix 8 Adverse Events of Special Interest**

Not Applicable.

**6.8. Appendix 9 Medications of Special Interest**

Not Applicable.

## **6.9. Appendix 10 Laboratory Toxicity Grading**

The grading scale use for lab assessments is based on ‘Common Terminology Criteria for Adverse Events (CTCAE) v5.0’.

If a laboratory value falls within the grading as specified below but also within the local laboratory normal limits, the value is considered to be normal and will be reset to grade 0.

Pre-baseline measurements will use the same grading ranges as applied to baseline measurements. In case a test has two sets of ranges – one for baseline normal and one for baseline abnormal, the one for baseline normal will be applied for all measurements taken pre-baseline and on baseline.

CTCAE Term	Grade 1	Grade 2	Grade 3	Grade 4	Janssen implementation notes
Blood and lymphatic system disorders					
Anemia	Hemoglobin (Hgb) <LLN - 10.0 g/dL; <LLN - 6.2 mmol/L; <LLN - 100 g/L	Hemoglobin (Hgb) <10.0 - 8.0 g/dL; <6.2 - 4.9 mmol/L; <100 - 80g/L	Hemoglobin (Hgb) <8.0 g/dL; <4.9 mmol/L; <80 g/L; transfusion indicated	Life-threatening consequences; urgent intervention indicated	Clinical signs and symptoms are not taken into consideration for grading.
Leukocytosis	-	-	>100,000/mm  ; >100 x 10e9 /L	Clinical manifestations of leucostasis; urgent intervention indicated	Clinical signs and symptoms are not taken into consideration for grading; Added ranges in SI unit (x 10e9 /L)
Investigations					
Activated partial thromboplastin time prolonged	>ULN - 1.5 x ULN	>1.5 - 2.5 x ULN	>2.5 x ULN; bleeding	-	Clinical signs and symptoms are not taken into consideration for grading.
Alanine aminotransferase increased	>ULN - 3.0 x ULN if baseline was normal; 1.5 - 3.0 x baseline if baseline was abnormal	>3.0 - 5.0 x ULN if baseline was normal; >3.0 - 5.0 x baseline if baseline was abnormal	>5.0 - 20.0 x ULN if baseline was normal; >5.0 - 20.0 x baseline if baseline was abnormal	>20.0 x ULN if baseline was normal; >20.0 x baseline if baseline was abnormal	Ranges defined for “abnormal baseline” are applied only if baseline > ULN. If baseline < LLN, then ranges for “normal baseline” are applied.
Alkaline phosphatase increased	>ULN - 2.5 x ULN if baseline was normal; 2.0 - 2.5 x baseline if baseline was abnormal	>2.5 - 5.0 x ULN if baseline was normal; >2.5 - 5.0 x baseline if baseline was abnormal	>5.0 - 20.0 x ULN if baseline was normal; >5.0 - 20.0 x baseline if baseline was abnormal	>20.0 x ULN if baseline was normal; >20.0 x baseline if baseline was abnormal	Ranges defined for “abnormal baseline” are applied only if baseline > ULN. If baseline < LLN, then ranges for “normal baseline” are applied.
Aspartate aminotransferase increased	>ULN - 3.0 x ULN if baseline was normal; 1.5 - 3.0 x baseline if baseline was abnormal	>3.0 - 5.0 x ULN if baseline was normal; >3.0 - 5.0 x baseline if baseline was abnormal	>5.0 - 20.0 x ULN if baseline was normal; >5.0 - 20.0 x baseline if baseline was abnormal	>20.0 x ULN if baseline was normal; >20.0 x baseline if baseline was abnormal	Ranges defined for “abnormal baseline” are applied only if baseline > ULN. If baseline < LLN, then ranges for “normal baseline” are applied.
Blood bilirubin increased	>ULN - 1.5 x ULN if baseline was normal;	>1.5 - 3.0 x ULN if baseline was normal;	>3.0 - 10.0 x ULN if baseline was normal;	>10.0 x ULN if baseline was normal;	Ranges defined for “abnormal baseline” are

CTCAE Term	Grade 1	Grade 2	Grade 3	Grade 4	Janssen implementation notes
	> 1.0 - 1.5 x baseline if baseline was abnormal	>1.5 - 3.0 x baseline if baseline was abnormal	>3.0 - 10.0 x baseline if baseline was abnormal	>10.0 x baseline if baseline was abnormal	applied only if baseline > ULN. If baseline < LLN, then ranges for “normal baseline” are applied.
CD4 lymphocytes decreased	<LLN - 500/mm  ; <LLN - 0.5 x 10  /L	<500 - 200/mm  ; <0.5 - 0.2 x 10  /L	<200 - 50/mm  ; <0.2 x 0.05 - 10e  /L	<50/mm  ; <0.05 x 10e  /L	
Cholesterol high	>ULN - 300 mg/dL; >ULN - 7.75 mmol/L	>300 - 400 mg/dL; >7.75 - 10.34 mmol/L	>400 - 500 mg/dL; >10.34 - 12.92 mmol/L	>500 mg/dL; >12.92 mmol/L	
CPK increased	>ULN - 2.5 x ULN	>2.5 x ULN - 5 x ULN	>5 x ULN - 10 x ULN	>10 x ULN	
Creatinine increased	Creatine Kinase >ULN - 1.5 x ULN	Creatine Kinase >1.5 - 3.0 x baseline; >1.5 - 3.0 x ULN	Creatine Kinase >3.0 x baseline; >3.0 - 6.0 x ULN	Creatine Kinase >6.0 x ULN	
Fibrinogen decreased	<1.0 - 0.75 x LLN; if abnormal, <25% decrease from baseline	<0.75 - 0.5 x LLN; if abnormal, 25 - <50% decrease from baseline	<0.5 - 0.25 x LLN; if abnormal, 50 - <75% decrease from baseline	<0.25 x LLN; if abnormal, 75% decrease from baseline; absolute value <50 mg/dL	Ranges defined for “abnormal” are applied only on values < LLN. Grade 0 will be assigned to values > ULN.
GGT increased	>ULN - 2.5 x ULN if baseline was normal; 2.0 - 2.5 x baseline if baseline was abnormal	>2.5 - 5.0 x ULN if baseline was normal; >2.5 - 5.0 x baseline if baseline was abnormal	>5.0 - 20.0 x ULN if baseline was normal; >5.0 - 20.0 x baseline if baseline was abnormal	>20.0 x ULN if baseline was normal; >20.0 x baseline if baseline was abnormal	Ranges defined for “abnormal baseline” are applied only if baseline > ULN. If baseline < LLN, then ranges for “normal baseline” are applied.
Haptoglobin decreased	<LLN	-	-	-	
Hemoglobin increased	Increase in >0 - 2 g/dL; Increase in >0 - 20 g/L	Increase in >2 - 4 g/dL; Increase in >20 - 40 g/L	Increase in >4 g/dL; Increase in >40 g/L	-	The increase indicates the level of increase above normal (above ULN). Applied as, e.g. grade 1 (g/dL): >ULN – ULN+2 g/dL; Added ranges in SI unit (g/L).
INR increased	>1.2 - 1.5; >1 - 1.5 x baseline if on anticoagulation; monitoring only indicated	>1.5 - 2.5; >1.5 - 2.5 x baseline if on anticoagulation; dose adjustment indicated	>2.5; >2.5 x baseline if on anticoagulation; bleeding	-	Concomitant therapy or clinical signs and symptoms are not taken into consideration for grading.

CTCAE Term	Grade 1	Grade 2	Grade 3	Grade 4	Janssen implementation notes
Lipase increased	>ULN - 1.5 x ULN	>1.5 - 2.0 x ULN; >2.0 - 5.0 x ULN and asymptomatic	>2.0 - 5.0 x ULN with signs or symptoms; >5.0 x ULN and asymptomatic	>5.0 x ULN and with signs or symptoms	“Asymptomatic” ranges are not taken into consideration for grading, i.e. worst case grading is applied.
Lymphocyte count decreased	<LLN - 800/mm  ; <LLN - 0.8 x 10  /L	<800 - 500/mm  ; <0.8 - 0.5 x 10  /L	<500 - 200/mm  ; <0.5 - 0.2 x 10  /L	<200/mm  ; <0.2 x 10  /L	
Lymphocyte count increased	-	>4000/mm  - 20,000/mm  ; >4 - 20 x 10  /L	>20,000/mm  ; >20 x 10  /L	-	Added ranges in SI unit (x 10  /L).
Neutrophil count decreased	<LLN - 1500/mm  ; <LLN - 1.5 x 10  /L	<1500 - 1000/mm  ; <1.5 - 1.0 x 10  /L	<1000 - 500/mm  ; <1.0 - 0.5 x 10  /L	<500/mm  ; <0.5 x 10  /L	Both Neutrophils and segmented neutrophils are graded using these criteria.
Platelet count decreased	<LLN - 75,000/mm  ; <LLN - 75.0 x 10  /L	<75,000 - 50,000/mm  ; <75.0 - 50.0 x 10  /L	<50,000 - 25,000/mm  ; <50.0 - 25.0 x 10  /L	<25,000/mm  ; <25.0 x 10  /L	
Serum amylase increased	>ULN - 1.5 x ULN	>1.5 - 2.0 x ULN; >2.0 - 5.0 x ULN and asymptomatic	>2.0 - 5.0 x ULN with signs or symptoms; >5.0 x ULN and asymptomatic	>5.0 x ULN and with signs or symptoms	“Asymptomatic” ranges are not taken into consideration for grading, i.e. worst case grading is applied.
White blood cell decreased	<LLN - 3000/mm  ; <LLN - 3.0 x 10  /L	<3000 - 2000/mm  ; <3.0 - 2.0 x 10  /L	<2000 - 1000/mm  ; <2.0 - 1.0 x 10  /L	<1000/mm  ; <1.0 x 10  /L	
Metabolism and nutrition disorders					
Acidosis	pH <normal, but $\geq 7.3$	-	pH <7.3	Life-threatening consequences	pH <normal is implemented as pH <LLN. Clinical signs and symptoms are not taken into consideration for grading.
Alkalosis	pH >normal, but $\leq 7.5$	-	pH >7.5	Life-threatening consequences	pH >normal is implemented as pH >ULN. Clinical signs and symptoms are not taken into consideration for grading.

CTCAE Term	Grade 1	Grade 2	Grade 3	Grade 4	Janssen implementation notes
Hypercalcemia	Corrected serum calcium of >ULN - 11.5 mg/dL; >ULN - 2.9 mmol/L;  Ionized calcium >ULN - 1.5 mmol/L	Corrected serum calcium of >11.5 - 12.5 mg/dL; >2.9 - 3.1 mmol/L;  Ionized calcium >1.5 - 1.6 mmol/L;  symptomatic	Corrected serum calcium of >12.5 - 13.5 mg/dL; >3.1 - 3.4 mmol/L;  Ionized calcium >1.6 - 1.8 mmol/L;  hospitalization indicated	Corrected serum calcium of >13.5 mg/dL; >3.4 mmol/L;  Ionized calcium >1.8 mmol/L;  life-threatening consequences	Clinical signs and symptoms are not taken into consideration for grading.
Hyperkalemia	Potassium >ULN - 5.5 mmol/L	Potassium >5.5 - 6.0 mmol/L;  intervention initiated	Potassium >6.0 - 7.0 mmol/L;  hospitalization indicated	Potassium >7.0 mmol/L;  life-threatening consequences	Clinical signs and symptoms are not taken into consideration for grading.
Hypermagnesemia	Magnesium >ULN - 3.0 mg/dL; >ULN - 1.23 mmol/L	-	Magnesium >3.0 - 8.0 mg/dL; >1.23 - 3.30 mmol/L	Magnesium >8.0 mg/dL; >3.30 mmol/L;  life-threatening consequences	Clinical signs and symptoms are not taken into consideration for grading.
Hypernatremia	Sodium >ULN - 150 mmol/L	Sodium >150 - 155 mmol/L;  intervention initiated	Sodium >155 - 160 mmol/L;  hospitalization indicated	Sodium >160 mmol/L;  life-threatening consequences	Clinical signs and symptoms are not taken into consideration for grading.
Hypertriglyceridemia	Triglycerides 150 mg/dL - 300 mg/dL; 1.71 mmol/L - 3.42 mmol/L	Triglycerides >300 mg/dL - 500 mg/dL; >3.42 mmol/L - 5.7 mmol/L	Triglycerides >500 mg/dL - 1000 mg/dL; >5.7 mmol/L - 11.4 mmol/L	Triglycerides >1000 mg/dL; >11.4 mmol/L;  life-threatening consequences	Clinical signs and symptoms are not taken into consideration for grading.
Hypoalbuminemia	Albumin <LLN - 3 g/dL; <LLN - 30 g/L	Albumin <3 - 2 g/dL; <30 - 20 g/L	Albumin <2 g/dL; <20 g/L	Life-threatening consequences; urgent intervention indicated	Clinical signs and symptoms are not taken into consideration for grading.
Hypocalcemia	Corrected serum calcium of <LLN - 8.0 mg/dL; <LLN - 2.0 mmol/L;  Ionized calcium <LLN - 1.0 mmol/L	Corrected serum calcium of <8.0 - 7.0 mg/dL; <2.0 - 1.75 mmol/L;  Ionized calcium <1.0 - 0.9 mmol/L;	Corrected serum calcium of <7.0 - 6.0 mg/dL; <1.75 - 1.5 mmol/L;  Ionized calcium <0.9 - 0.8 mmol/L;	Corrected serum calcium of <6.0 mg/dL; <1.5 mmol/L;  Ionized calcium <0.8 mmol/L;	Clinical signs and symptoms are not taken into consideration for grading.

CTCAE Term	Grade 1	Grade 2	Grade 3	Grade 4	Janssen implementation notes
		symptomatic	hospitalization indicated	life-threatening consequences	
Hypoglycemia	Glucose <LLN - 55 mg/dL; <LLN - 3.0 mmol/L	Glucose <55 - 40 mg/dL; <3.0 - 2.2 mmol/L	Glucose <40 - 30 mg/dL; <2.2 - 1.7 mmol/L	Glucose <30 mg/dL; <1.7 mmol/L; life-threatening consequences; seizures	Clinical signs and symptoms are not taken into consideration for grading. Urine glucose is not graded.
Hypokalemia	Potassium <LLN - 3.0 mmol/L	Symptomatic with Potassium <LLN - 3.0 mmol/L; intervention indicated	Potassium <3.0 - 2.5 mmol/L; hospitalization indicated	Potassium <2.5 mmol/L; life-threatening consequences	“Symptomatic” ranges are applied for grade 2, grade 1 not assigned, i.e. worst case applied. Clinical signs and symptoms are not taken into consideration for grading of grade 3 and 4.
Hypomagnesemia	Magnesium <LLN - 1.2 mg/dL; <LLN - 0.5 mmol/L	Magnesium <1.2 - 0.9 mg/dL; <0.5 - 0.4 mmol/L	Magnesium <0.9 - 0.7 mg/dL; <0.4 - 0.3 mmol/L	Magnesium <0.7 mg/dL; <0.3 mmol/L; life-threatening consequences	Clinical signs and symptoms are not taken into consideration for grading.
Hyponatremia	Sodium <LLN - 130 mmol/L	Sodium 125-129 mmol/L and asymptomatic	Sodium 125-129 mmol/L symptomatic; 120-124 mmol/L regardless of symptoms  Sodium <130-120 mmol/L	Sodium <120 mmol/L; life-threatening consequences	Clinical signs and symptoms are not taken into consideration for grading. Worst case (“<130-120 mmol/L” for grade 3 added by Janssen) is applied across grade 2/3 ranges: 120-129 mol/L assigned to grade 3, grade 2 not used.
Renal and urinary disorders					
Proteinuria	1+ proteinuria; urinary protein $\geq$ ULN - <1.0 g/24 hrs; urinary protein $\geq$ ULN - <1000 mg/day	Adult: 2+ and 3+ proteinuria; urinary protein 1.0 - <3.5 g/24 hrs;	Adult: 4+ proteinuria; urinary protein $\geq$ 3.5 g/24 hrs;	-	In case both 24-h urine collection and dipstick are collected, then worst case is taken, as opposed to having 24-h urine

CTCAE Term	Grade 1	Grade 2	Grade 3	Grade 4	Janssen implementation notes
		urinary protein 1000 - <3500 mg/day  Pediatric: Urine P/C (Protein/Creatinine) ratio 0.5 - 1.9; Urine P/C (Protein/Creatinine) 56.5 – 214.7 g/mol	urinary protein $\geq$ 3500 mg/day;  Pediatric: Urine P/C (Protein/Creatinine) ratio $>$ 1.9; Urine P/C (Protein/Creatinine) $>$ 214.7 g/mol		collection take precedence over dipstick. Added ranges in SI unit for urinary protein (mg/day) and for urine P/C (g/mol). Pediatric grading is applied to age range [0-18]. Adult grading is applied for ages [ $>$ 18].

\* Grade 0 is assigned to a lab assessment when the lab test is described in the table, but the lab value is not assigned a grade 1 or higher.

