### **Clinical Laboratory Tests**

Laboratory data will be summarized by type of laboratory test (eg, hematology, clinical chemistry). Selected laboratory parameters will be summarized by treatment groups. Common Terminology Criteria (CTC) will be used to identify abnormal laboratory test results, and the incidence and severity of abnormal laboratory parameters (hematology and chemistry) will be summarized by treatment group.

In addition, a listing of participants with Grade 2 or higher laboratory test results (based on the CTC criteria) will also be provided.

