#### Protocol-Required Safety Laboratory Assessments

Laboratory Assessments	Parameters		
Hematology	Platelet count Red blood cell count Hemoglobin Hematocrit	RBC Indices: MCV MCH % Reticulocytes	White Blood Cell (WBC) count with Differential: Neutrophils Lymphocytes Monocytes Eosinophils Basophils
Clinical Chemistry	Sodium Potassium Chloride Bicarbonate Blood urea nitrogen (BUN) Creatinine Glucose Aspartate aminotransferase (AST)/Serum glutamic-oxaloacetic Alanine aminotransferase (ALT)/Serum glutamic-oxaloacetic	Total bilirubin Indirect bilirubin Alkaline phosphatase Calcium Phosphate Albumin Total protein Lactate dehydrogenase (LDH)	

Note: Details of the liver chemistry stopping criteria and required actions and follow-up are given in Section 10.19, Liver Safety.
 
Potential Hy's Law case (ALT or AST <math>\geq 3</math> x ULN and Tbili <math>\geq 2</math> x ULN) reporting requirements are defined in Section 8.3.1.
			
Other Laboratory Tests	
 
• Urine pregnancy testing for women of childbearing potential only
 
• Serum Pregnancy Testing for women of childbearing potential only (at Screening only)
 
• Lipids (Week 0 only: Part 1)
 
• Fasting lipid panel: high-density lipoprotein, low-density lipoprotein (calculated), total cholesterol, triglycerides (Weeks 0, 1, and 12: Part 2)
 
• High-sensitivity C-reactive protein
 
 
Serology (HIV antibody, hepatitis B surface antigen [HBsAg], hepatitis B surface antibody [anti-HBs], hepatitis B core antibody [anti-HBc], and hepatitis C virus antibody)
		

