	
 
• Change in number of inflammatory nodules from baseline to Week 16 in Part 1, and at Week 12 in Part 2.
 
• Change of International Hidradenitis Suppurativa Severity Score System (IHS4) score from baseline to Week 16 in Part 1, and at Week 12 in Part 2.
 
• Proportion of participants with HS-Investigator's Global Assessment (HS-IGA) score of inactive (0), almost inactive (1), or mild (2) and with at least 2-grade improvement relative to baseline at Week 16 in Part 1, and at Week 12 in Part 2.
 
• Proportion of participants with HS-IGA score of inactive (0) or almost inactive (1) at Week 16 in Part 1, and at Week 12 in Part 2 among participants with HS-IGA score of moderate (3) or severe (4) at baseline.
 

 
• To characterize additional patient-reported outcome efficacy measures of bermekimab in participants with moderate to severe HS.
 
	
 
• Change in Dermatology Life Quality Index (DLQI) score from baseline to Week 16 in Part 1, and at Week 12 in Part 2.
 
• Change in Hidradenitis Suppurativa Symptom Diary (HSSD-24h) score from baseline to Week 16 in Part 1, and at Week 12 in Part 2.
 
• Change in pain scale score of HSSD-24h from baseline to Week 16 in Part 1, and at Week 12 in Part 2.
 
• Change in itch scale score of HSSD-24h from baseline to Week 16 in Part 1, and at Week 12 in Part 2.
 

 
• To assess the safety and tolerability of bermekimab in participants with moderate to severe HS.
 
	
 
• Number/proportion of participants with treatment-emergent adverse events (TEAEs).
 
• Number/proportion of participants with treatment-emergent serious adverse events (SAEs).
 
• Number/proportion of participants with abnormal safety laboratory values.
 

 
• To evaluate the pharmacokinetics (PK) and immunogenicity of bermekimab in participants with moderate to severe HS.
 
	
 
• Bermekimab concentration will be summarized for treated participants over time.
 
• The incidence of antibodies to bermekimab will be summarized.
 

Exploratory	

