### **5.6.3. Additional Safety Assessments**

#### **5.6.3.1. Clinical Laboratory Tests**

Clinical laboratory tests will be displayed for the participants included in the safety analysis set.

Descriptive statistics of change from baseline through Week 36 will be summarized for selected chemistry, and hematology tests and displayed by intervention group.

- **Hematology** will include but are not limited to the following: Basophils, Eosinophils, Hemoglobin, Lymphocytes, Monocytes, Neutrophils, Platelets, WBC, CRP and ESR.
- **Chemistry** will include but are not limited to the following: ALT, AST, Albumin, Alkaline Phosphatase, Bicarbonate (CO2), Calcium, Chloride, Creatinine, GGT, Glucose, Potassium, SGOT, SGPT, Sodium, Total Bilirubin, Total Protein, Urea Nitrogen.

Applicable laboratory results will be graded according to National Cancer Institute's Common Terminology Criteria for Adverse Events (NCI-CTCAE). Participants with toxicity grades  $\geq 2$  will be listed.

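### SAP Appendix 10 names creatine kinase in all four grade cells of the creatinine row, so serum creatinine has no correctly worded rule for the Grade 2 or higher listing

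*SAP*

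**What the plan says.** SAP Section 6.9 (Appendix 10) sets out the laboratory grading table. It opens with "The grading scale use for lab assessments is based on" CTCAE v5.0 and then gives cut-offs test by test.

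- The row labelled *Creatinine increased* names creatine kinase in the Grade 1, 2, 3 and 4 cells. The Grade 2 cell is "Creatine Kinase >1.5 - 3.0 x baseline; >1.5 - 3.0 x ULN". The implementation-notes cell for the row is empty.
- The row directly above, *CPK increased*, grades creatine phosphokinase. Its Grade 2 cell is ">2.5 x ULN - 5 x ULN".
- The table footnote says that "Grade 0 is assigned to a lab assessment when the lab test is described in the table" and no grade of 1 or higher has been reached.

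Serum creatinine is a routine test in this trial. Protocol Appendix 3 (Section 10.3) includes it in the chemistry panel ("Blood urea nitrogen (BUN) Creatinine Glucose"), and SAP Section 5.6.3.1 names it among the tests to be summarised ("Calcium, Chloride, Creatinine, GGT, Glucose, Potassium").

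The grades feed one laboratory output. SAP Section 5.6.3.1 lists participants with toxicity Grade 2 or higher, and Protocol Section 9.4.3 says "a listing of participants with Grade 2 or higher laboratory test results (based on the CTC criteria) will also be provided". The related secondary safety endpoint in SAP Section 1.1 is "Number/proportion of participants with abnormal safety laboratory values".

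**The concern.** The cells contradict their own row label. They give one enzyme two different scales and leave a scheduled kidney-function test with no cell that names it. In this table the analyte named in a cell tells the programmer which test to grade: the anemia row names hemoglobin, and the potassium and sodium rows name those electrolytes. The wording is therefore operative.

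At stake is the completeness of the Grade 2 or higher listing. The protocol also planned summaries of the incidence and severity of abnormal laboratory parameters. After the decision to terminate, SAP Appendix 2 (Section 6.2) reduced the safety analyses, and Section 5.6.3.1 now specifies only change-from-baseline statistics and this listing. The listing is thus the one grade-based laboratory output left in the SAP. A participant with raised creatinine who is missing from it would not be identified by a group summary of change from baseline.

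**Working it through.** The plan states no figure to reproduce, so the check is a comparison of text followed by application of the row's own cut-offs.

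**Step 1. The two rows side by side (multiples of ULN, SAP Section 6.9).**

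| Grade | *CPK increased* | *Creatinine increased* (cells name creatine kinase) |
|---|---|---|
| 1 | >1 to 2.5 | >1 to 1.5 |
| 2 | >2.5 to 5 | >1.5 to 3.0 |
| 3 | >5 to 10 | >3.0 to 6.0 |
| 4 | >10 | >6.0 |

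The second row also has baseline multiples: >1.5 to 3.0 times baseline for Grade 2 and >3.0 times baseline for Grade 3.

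**Step 2. Is this an artefact of reading the PDF?** That is unlikely. The same wrong analyte appears in four separate cells, each with its cut-offs intact.

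**Step 3. Is serum creatinine graded anywhere else?** No. The only other mention of creatinine in the table is the pediatric urine protein/creatinine ratio under proteinuria.

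**Step 4. Effect on illustrative creatinine values, using the ULN part of the row.** The values are chosen only to fall in each grade band. All exceed ULN, so the appendix's rule resetting values within normal limits to Grade 0 does not apply.

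| Creatinine | Cells read literally | Analyte corrected | In the Grade 2 or higher listing: literal / corrected |
|---|---|---|---|
| 1.2 x ULN | Grade 0 or no grade | Grade 1 | no / no |
| 2 x ULN | Grade 0 or no grade | Grade 2 | no / yes |
| 4 x ULN | Grade 0 or no grade | Grade 3 | no / yes |
| 8 x ULN | Grade 0 or no grade | Grade 4 | no / yes |

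Of the three values that should be listed, 0 of 3 are listed on the literal reading and 3 of 3 after correction. The literal result depends on the footnote. If the row label counts as describing creatinine in the table, the footnote assigns Grade 0, because no cell gives creatinine a higher grade. If it does not count, there is no grade. Neither outcome reaches the listing.

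**Step 5. How often the rule is used.** The Part 1 schedules (Protocol Sections 1.3.1 and 1.3.3) draw chemistry at Weeks 2, 4, 8, 12 and 16 and at Weeks 20, 24, 28, 32 and 36. That is 5 + 5 = 10 scheduled post-baseline draws for a participant who completes the planned schedule.

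**Step 6. Side effect on creatine kinase.** Read literally, the two rows give this enzyme different grades at >1.5 to 2.5 x ULN (1 against 2), >3 to 5 x ULN (2 against 3) and >6 to 10 x ULN (3 against 4). This matters little: the enzyme is in neither chemistry list and is requested only in liver-event follow-up (Protocol Section 10.19.2).

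**The case against.** The strongest reply is that nobody would be misled. The row label says creatinine, the row above already covers the enzyme, and the appendix cites CTCAE v5.0. SAP Section 5.6.3.1 sends the grading to the NCI criteria in general without citing Appendix 10, and the protocol likewise bases its listing on those criteria. A programmer would probably apply the cut-offs to serum creatinine, and the listing would then be unchanged.

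Other points limit the effect further:

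- Screening creatinine is capped at 1.5 mg/dL, and the documents give no expected frequency of raised values.
- The 10 draws are a planned maximum, in a study whose termination was decided on 14 October 2022.
- The secondary endpoint is a number or proportion, whereas the affected output is a listing.
- Change from baseline in creatinine is summarised through Week 36. Clinically relevant laboratory changes are recorded as adverse events (Protocol Section 8.2.4) and tabulated (SAP Section 5.6.2).

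Most of this stands, and it keeps the point small. It does not make the table right. The general CTCAE reference shows what was meant, but Appendix 10 is the SAP's own written grading table. Someone checking the listing against it must either depart from its text or leave raised creatinine out. The two safeguards are also not equivalent to the listing: group statistics do not identify individuals, and adverse event entry depends on the investigator's judgement of clinical relevance.

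**Conclusion.** The concern holds as a drafting error. All four grade cells of the creatinine row name the wrong analyte, and no other row supplies a rule for serum creatinine. Followed to the letter, the table leaves raised creatinine out of the Grade 2 or higher listing: 0 of 3 illustrative values are listed, against 3 of 3 once corrected.

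That size rests on two assumptions: that the cells are applied literally, and that the row's cut-offs are the intended ones for creatinine. The grading program is not in the documents, so what was actually programmed is unknown. The number of participants with raised creatinine is not given either. If the program already follows the row label, the listing does not change.

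The output is descriptive, other outputs still carry part of the creatinine signal, and efficacy conclusions are unaffected. The correction should be made, but it is minor.

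**What to change.** 1. In SAP Appendix 10, in the *Creatinine increased* row, replace creatine kinase with creatinine in all four grade cells.
2. Confirm that row's cut-offs against CTCAE v5.0, the source the SAP cites. They were not checked against it here, because it lies outside the documents.
3. Grade creatine kinase only by the *CPK increased* row.
4. Check the grading program against the corrected row before the Grade 2 or higher listing is produced.

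The cost is a one-row text correction and one program check. No new data are needed.
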